2. RESEARCH PLAN

Purpose of Study:
The primary aim of this study is to see if the use of an antiseptic preparation (povidone iodine) versus cold normal saline, will decrease rates of urine contamination during the non-invasive Quick Wee (QW) collection of pediatric urine.
Hypotheses, Research Questions, or Objectives:
To evaluate two different cleansing solutions in controlling urine contamination.
Significance
If the use of antiseptic preparation decreases the level of contamination in this study then it would provide an effective and reliable clean catch method that staff could utilize prior to electing for catheterization or suprapubic aspiration.
Military Relevance:
Having a noninvasive Quick Wee method with a high 5 minute void success rate; patient wait times in the emergency department will decrease, and parents will be happier with avoiding invasive measures. This improves patient safety, and provides the clinician with another method for collecting urine. In the Air Force's move towards a culture of safety, and zero harm; further evaluation into this novel technique's reliability will support our goals provided rates of urine contamination can be minimized. The importance of researching noninvasive methods with low levels of contamination is that it may prevent further invasive methods from being used. For example if a child's urine specimen from clean catch is contaminated the next step would be to get the sample via catheterization, a method that is traumatic to child, parent and sometimes staff. If research shows that urogenital prep with iodine decreases level of contamination in the urine then it provides an acceptable method of urine clean catch collection.
Background and Review of Literature:
Urinary tract infections (UTI) are common acute illnesses among pediatric patients, accounting for 5-7% of emergency department visits in the under two-year-old population [1]. However, obtaining urine samples from the precontinent patient can be difficult. There is an ongoing debate regarding which noninvasive method for urine specimen collection is best for this population. The main argument against clean catch is the high rate of contamination compared to invasive collection and reliability.

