Children will then have their periurethral region gently cleansed for ten seconds with one of the previously discussed solutions. The procedure requires cold saline (approximately 2°C) soaked gauze to be applied in a circular motion over the bare suprapubic region of the child continuously for five minutes. The saline will come in the form of sterile saline flushes kept in a cooler of ice in the departments were the study is being conducted.

If the child voids within five minutes the time in seconds will be recorded on the provided worksheet. Also whether or not the urine was successfully “caught” in the specimen cup will be documented. Whether or not the sample was contaminated by lab standards will also be recorded on the data sheet once the results are available.

At the conclusion of the child's participation, the parents will be asked to complete a Satisfaction Survey asking their overall satisfaction with the collection method utilized.						
a. Interventions and Observations:						
The primary outcome of this study is to evaluate whether there is an improvement in the rate of urine contamination with iodine solution over normal saline prior to the QW. The secondary outcome will be the QW's rate of success in providing a CCU in five minutes.						
b. Setting:						
This study will be conducted at the 99MDG at Nellis AFB. Children will be recruited from the emergency department as well as the pediatric clinic through parental permission and consent. Research Staff will enroll children through parental authorization, based on the child's age, and if a standard of care urinalysis will be needed during their course of treatment, based on the determination of the child's attending physician. If a urinalysis is not needed as a course of treatment for the infant, the child will not be accepted for the study.						
c. Date(s):						
11 January 2019 – 31 May 2019						
d. Subjects:						
The sample population for this study are DoD beneficiary children from 28 days of age to 12 months requiring a standard of care urinalysis procedure as a course of treatment. They will be patients enrolled at 99MDG for evaluation and treatment. Children will be recruited from the pediatric clinic as well as the emergency department through parental permission and consent.						
e. Inclusion/Exclusion Criteria:						

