DoD ID# & FMP code						
Coding Plan?						
Describe the method that will be used		Each participant will be assigned a patient identifier starting with either A or B to				

to create and assign unique study codes to data.	show which group they were a member of and number 01-60 following the letter.		
Describe the method that will be used to create and assign unique study codes to specimens.	Urine specimens will be associated with the child's DoD ID# and FMP code for the initial results from the hospital laboratory and then the microscopy results will be put into the work book and the original results will be shredded. On the work book the results will assigned to the child's study code.		
What is the format of the key?	 Electronic		
Who will have access to the key?	Research Coordinators and Investigators		
Where will the key be stored and how will it be protected?	Location(s): All research data will be kept separately from the Master Key of coded, identifiable PHI/PII in an electronic database, which will be encrypted, double password protected and the access will be restricted. At the conclusion of the study, the research data will be de-identified prior to review and analysis. Confidentiality measures: The research data will be coded to mask the identity of the child. The code will be retained until the conclusion of the research study. Once a Final Report has been approved by the IRB, all the paper records will be stored and destroyed in accordance with the Long Term Storage Plan. The anonymized research data will not be utilized for further research activity beyond the protocol stipulations without additional IRB approval. At the end of all data mergers, or no later than at the closure of the study, all identifiable patient information will be destroyed based on AFI 33-332, "The Air Force Privacy and Civil Liberties Program" and the National Institute of Standards and Technology Special Publication (NIST SP 800-88) for the approved methods to destroy PII.		
Source of Research Material per Participant (Procedures)	# Routine Care	# Research Driven	# Total Procedures
Urine specimen	1	0	1
Participant Data Sheet completed by research staff	0	1	1
Satisfaction survey (Parent)	0	1	1

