Parent consent will be acquired via the written consent forms prior to the initiation of any research activities.

Benefits:

There may be decreased levels of urine contamination in either the saline or the iodine prep group's urine sample. If so, this will give a child's treatment team more reliable test results and decrease the need for more invasive urine testing. Additionally the normal saline preparation may be effective at decreasing the level of contamination as the iodine, this is the benefit of using normal saline for a preparation and comparing it to the iodine.

Risks:

Procedure is safe and the only possible negative outcome could be skin irritation from the iodine prep group. There are risks that urine sample may show that there was growth of bacteria on culture in which event the parents will be contacted by the PI or AI and made aware of these results and will be advised to follow up with their pediatrician. There is a possibility that the child has an allergic reaction to the iodine swab. If this occurs, the child will be referred to their pediatric PCM. The urine sample collected during the QW procedure will still be used for the study. There may be a risk of inadvertent breach of confidentiality.

Costs: None

Safeguards for Protecting Information:

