	Specimens	Urine samples will be disposed of by the lab after analysis is complete. Results will be acquired through CHCS using the child's DoD ID# and name. DoD ID# will be used initially for urinalysis results tracking and then Study code IDs will be used for de-identified research data
	Long-term storage (following completion of the study and inactivation of IRB approval)	The research data will be coded and any links to identifiable data will be destroyed (an approved shredding bin) as soon as possible or no later than at the closure of the study, with the exception of those parents that consented to place their child's de-identified research data into the "Mike O'Callaghan Military Medical Center General Research Data Repository" (FWH20180064H) for future research. The anonymized

		research data will not be utilized for further research activity beyond the protocol stipulations without additional IRB approval. All de-identified research data will be maintained for 3 years following study closure.
--	--	--

Safeguards for Protecting Subjects Relative to Reasonably Expected Risks:

The principal investigator will be responsible for the protocol safety monitoring. The PI will make study documents (e.g., consent forms, data pulls) and pertinent hospital or clinical records readily available for inspection by the 59 MDW IRB and over sight staff for confirmation of the study data. If at any time the parent reports a side effect being experienced by their child, they will be referred to one of the Investigators for care or to the child's pediatric PCM.

Categories of subjects

Children (17 yrs or less), includes viable neonates (28 days of age to 12 months)

Clinical Care:

All children will receive standard of care regardless of inclusion into this study. If at any time a child experiences any injury or adverse effects, appropriate clinical care will be given or the child will be referred to appropriate provider. If a urine sample should be abnormal the PI or AI will follow up with the child's parents and ensure they either follow up with their primary care provider or report to the emergency department, if symptomatic.

Injury Compensation: N/A**Data Safety Monitoring**

N/A – none of the situations listed above apply

5. ALTERNATIVES**Alternatives:**

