The alternatives for QW urine collection are urine specimen collection by using the bag specimen collection method or the invasive straight catheterization or suprapubic aspiration. The alternative to using an iodine cleansing solution is to use a normal saline solution. The parents also have the authority to deny their child's participation in the study.

6. DATA ANALYSIS**Data Analysis:**

Primary analysis will be performed by intent-to-treat including all randomized children, where primary outcome data are available, consistent with the CONSORT guidelines for intention to treat analysis. The primary outcome measure is a binary yes/no outcome of detection of microbial markers to determine level of contamination. The absolute difference between the two groups will be reported so that the percentage of contamination samples, together with the 95% CI for the differences of percentages, and calculate p values using a chi squared test. A p value of <0.05 will be considered significant. For the secondary outcome there will also be a measure of binary yes/no outcome of voiding urine within 5 minutes. The rate of successful voiding within 5 min will be described for each group with percentages and 95% CI. The p value will be estimated using chi squared test for categorical variables and t-test or Wilcoxon's rank sum tests for continuous variables.

Additionally we will also be evaluating patient's gender, and age in months for comparative data analysis to help strengthen the study's statistical design outcomes.

Outcome Measures:

Level of urine contamination (binary yes or no), if there was a sample collected in 5 minutes (binary yes or no), and time to void with a 300 second cap are the two outcome measures being evaluated in this study.

Sample Size Estimation/Power Analysis:

This is a pilot study and will have a relatively low sample of 60 subjects.

Statistical Analysis:

Data analysis will be conducted by Baylor University statistics department ([name])

Number of Subjects:	# Planned to Enroll	# Enrolled	# Planned to Complete Study	TOTAL
----------------------------	----------------------------	-------------------	------------------------------------	--------------

Number of Subjects at 99 MDG	60	0	60	60
------------------------------	----	---	----	----

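### Do the two wordings of the primary outcome, microbial markers and contamination by lab standards, leave infected samples scored as contaminated?

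*Combined protocol and SAP*

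**What the plan says.** The outcome is described in three places.

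- Section 6, Data Analysis: "The primary outcome measure is a binary yes/no outcome of detection of microbial markers to determine level of contamination". The next sentence promises the absolute difference between groups in the percentage of contaminated samples, with a 95% confidence interval and a chi-squared p value.
- Section 6, Outcome Measures: "Level of urine contamination (binary yes or no", with no criterion attached.
- Section 3, Research Design and Methods: "Whether or not the sample was contaminated by lab standards will also be recorded on the data sheet" once results are available.

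Four passages bear on the laboratory test.

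- Section 3.b, Setting, makes enrolment depend on "if a standard of care urinalysis will be needed during their course of treatment".
- Section 3.f, Coding Plan, says "the microscopy results will be put into the work book".
- Section 4, Data and Specimen Storage Plan, says "DoD ID# will be used initially for urinalysis results tracking".
- Section 4, Risks, mentions "growth of bacteria on culture in which event the parents will be contacted".

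Section 12 lists a Participant Data Sheet and a Lab Letter of Support as attachments. Neither is in the available text.

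**The concern.** Nothing says that the Section 6 outcome and the Section 3 data-sheet entry are the same variable. No organism, threshold or category for infection is given. These children are tested because a clinician wants a urine sample, so some will be infected, and the Risks text treats growth on culture as something parents must be told about. An infected urine contains microbes. If detection alone decided the outcome, it would be scored as contaminated.

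Cleansing the skin cannot be expected to remove an existing infection. Such samples would raise the percentage in both arms, pull the ratio of percentages towards 1 and widen the interval around the difference. With urinalysis, microscopy and culture all mentioned, it also seems possible that two analysts would build different primary variables.

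**Working it through.** **Do the wordings conflict?** The plan gives no power or effect size, so there is no figure of its own to reproduce. The first check is of the text.

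1. The Section 6 sentence does not stop at detection. It says what detection is for: determining contamination.
2. The sentence after it reports contaminated samples, and Outcome Measures names contamination as the yes/no variable.
3. Section 3 says what is written on the data sheet: the laboratory's contamination result.

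The markers are the means, and the laboratory standard is the judgement. No passage tells anyone to score an infected sample as contaminated, and nothing shows that the two phrases would classify any sample differently. On the source test, microscopy can be part of a urinalysis, so those mentions need not conflict. Culture appears once, about telling parents and not about the endpoint.

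**What if the strained reading were used?** Inputs:

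- Contamination with saline, c1 = 0.27 (Section 2, Background, for Quick-Wee).
- Contamination with iodine, c0 = 0.10 (assumption; not in the documents).
- Infection, u = 0.06 in both arms, independent of contamination (assumption). The nearest figure is "accounting for 5-7% of emergency department visits in the under two-year-old population", which concerns visits and not tested samples.
- 30 samples per arm (assumes equal allocation of 60 and a sample from every child), or 9.3 per arm if 31% void within five minutes as in the Background: 0.31 × 60 / 2.

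*Rule A, any infected or contaminated sample counts:* p = 1 − (1 − c)(1 − u).

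- Saline: 1 − 0.73 × 0.94 = 0.3138.
- Iodine: 1 − 0.90 × 0.94 = 0.1540.
- Difference 0.1598; ratio 0.154 / 0.3138 = 0.49.

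*Rule B, infected samples never count:* p = c(1 − u).

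- Saline: 0.27 × 0.94 = 0.2538.
- Iodine: 0.10 × 0.94 = 0.0940.
- Difference 0.1598; ratio 0.094 / 0.2538 = 0.37.

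Algebraically, both differences equal (1 − u)(c1 − c0), here 0.94 × 0.17 = 0.1598. The equality holds for any u and any pair of contamination rates. Against contamination counted regardless of infection (17.0 points), both rules lose the same amount: 1.0 point at u = 0.06, or 0.9 and 1.2 points at 0.05 and 0.07.

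*Precision*, as 1.96 × √(Σp(1 − p)/n). The sums are 0.3456 for A and 0.2746 for B.

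| Samples per arm | Rule A half-width | Rule B half-width |
|---|---|---|
| 30 | 21.0 points | 18.8 points |
| 9.3 | 37.8 points | 33.7 points |

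The second row is only rough, because the expected iodine-arm count is about one (9.3 × 0.154 = 1.4, or 9.3 × 0.094 = 0.9).

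*Infected samples expected in the whole trial:* 60 × 0.06 = 3.6 if every child gives a sample, and 60 × 0.31 × 0.06 = 1.1 if 31% do.

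**The case for a change.** The strongest case for a change is practical. The trial is not blinded, so an open criterion could be settled by people who know the allocation. The original laboratory results are to be shredded after transcription, and identifying links are destroyed by closure, so later re-scoring may be impossible. Infection among children selected for testing could exceed 6%. At an assumed 20%, Rule A gives 41.6% v 28.0%. With 30 per arm and 6% infection, exact chi-squared power is about 31% under Rule A and 38% under Rule B.

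Part of this stands: the protocol body does not state the criterion, the test or how infected samples are handled. The rest is weaker. The recorded result follows a laboratory standard. By the identifier table in Section 3.f, specimen containers carry names, dates and ID numbers but not the study code, whose first letter shows the group, so the label does not reveal the arm. The documents do not otherwise say that the laboratory is blinded. At 20% infection the difference is still 13.6 points under both rules (0.80 × 17). The power gain disappears at 9 per arm, where it is 11.3% under Rule A and 9.2% under Rule B. Rule B also assumes that the laboratory never calls an infected sample contaminated, which the documents do not show.

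**Conclusion.** No change to the plan follows. The two wordings are compatible, and an analyst following the text would use the laboratory-standard result already planned for the data sheet. If the strained reading were adopted anyway, the planned absolute difference would match that from excluding infections, 16.0 points in the illustration. The visible cost would fall on a ratio the plan never reports and on an interval about 2 points wider on each side at 30 per arm. Those sizes depend on an assumed iodine rate, an assumed infection rate and an unknown laboratory standard. The equality of the differences needs only that infection is equally common in both arms and independent of contamination.

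The unstated test and criterion are missing detail that the unseen data sheet or laboratory letter may supply, although the body does not point to either for a definition. A rewritten outcome would adopt a variable already planned, and separating out infected samples would need an infection criterion that appears nowhere in the documents. A sentence linking the two sections would be a courtesy to readers and would not alter the analysis.

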7. STUDY DURATION

Duration of Study:
Approximate duration of the study: four months

8. LOCAL AND EXTERNAL SUPPORT SERVICES

Local and External Support Services: None	
Describe the plan for training/informing clinical personnel about the study.	Who will you train?  Other: Nursing staff who will perform the QW and urine collection and will be instructed when to use an iodine swab or saline flush to cleanse the periurethral area. When will you provide the training?  Prior to the first subject being enrolled. How will you provide the training?  In person

9. INTRAMURAL (GME) AND EXTRAMURAL FUNDING SUPPORT

Intramural (GME) and Extramural Funding Support: None
--

10. DRUGS, BIOLOGICS, DIETARY SUPPLEMENTS, AND MEDICAL DEVICES

Is this research an “applicable clinical trial” which must be registered on ClinicalTrials.gov ?  No

Use of a placebo in place of standard therapy:		
Is a placebo being used in place of standard therapy?	 No	 Yes

11. MEDICAL RESEARCH AREA

 Emergency medicine	 Pediatrics
--	--

12. ATTACHMENTS

1. Form A, Signature Sheet
2. Form A-2, Study Personnel Listing
3. Form D, Informed Consent Document
4. E-1 Parental HIPAA Authorization Form
5. H23 Template, Research Involving Children Form
6. Recruitment Flyer
7. Participant Data Sheet
8. Lab Letter of Support
9. Flow Chart QW
10. Application Checklist
